6.2.3. Physical and Laboratory Test Findings

1. Evidence of organ dysfunction or any clinically significant deviation from normal in physical examination, vital signs, ECG, or clinical laboratory determinations beyond what is consistent with the target population.
2. Clinically significant abnormality on 12-lead ECG prior to study treatment administration, confirmed by repeat.
3. Total bilirubin, alanine aminotransferase (ALT), or aspartate aminotransferase (AST) greater than 2 times the upper limit of normal (ULN), confirmed by repeat. Elevated total bilirubin suspected to be due to Gilbert syndrome should be discussed with the Medical Monitor.
4. Serum creatinine $>168 \text{ mol/L}$ (1.9 mg/dL), confirmed by repeat.
5. Hematocrit $<30\%$, absolute neutrophil cell count of $\leq 1500/\mu\text{L}$ (with the exception of a documented history of a chronic benign neutropenia), or platelet cell count of $<120,000/\mu\text{L}$, or International normalized ratio (INR) >1.4 or other coagulopathy, confirmed by repeat. (Note: Participants with INR >1.4 due to antiplatelet/anticoagulant medications are eligible.)
6. A clinically significant abnormal thyroid-stimulating hormone test.
7. [REDACTED]
8. Hemoglobin A1C (HbA1C) $>8\%$, confirmed by repeat.

6.2.4. Allergies and Adverse Drug Reaction

1. History of allergy, hypersensitivity, or serious adverse reaction to mAbs or related compounds.
2. Allergy to any of the components of the study treatment, such as Polysorbate 80.
3. History of any significant drug allergy (such as anaphylaxis or hepatotoxicity).

CONFIDENTIAL

The information contained herein may not be used, disclosed, or published without the written consent of Biogen MA Inc.

6.2.5. Other Exclusion Criteria

1. Prisoners or participants who are involuntarily incarcerated. (Note: under certain specific circumstances a person who has been imprisoned may be included or permitted to continue as a participant. Strict conditions apply and Biogen approval is required.)
2. Participants who are compulsorily detained for treatment of either a psychiatric or physical (e.g., infectious disease) illness.

Eligibility criteria for this study have been carefully considered to ensure the safety of the study participants and that the results of the study can be used. It is imperative that participants fully meet all eligibility criteria.

6.3. Lifestyle Restrictions

Participants who are active tobacco smokers should not currently be smoking more than 10 cigarettes per day.

6.4. Screen Failures

Screen failures are defined as participants who consent to participate in the clinical study but are not subsequently randomized. A minimal set of screen failure information is required to ensure transparent reporting of screen failure participants, to meet the Consolidated Standards of Reporting Trials publishing requirements, and to respond to queries from regulatory authorities. Minimal information includes date of consent, demography, screen failure details, eligibility criteria, and any SAEs.

6.4.1. Retesting During Screening or Lead-In Period

Participant Re-screening: This study permits the re-screening of a participant who screen-failed up to 2 times (i.e., participant was not randomized or treated). If re-screened, the participant must be re-consented. The assessments to be conducted on re-screening will depend upon how much time passed since the previous Screening Visit. Please contact the Medical Monitor for guidance regarding the acceptability of any previous assessments completed.

Retesting of laboratory parameters and/or other assessments within any single screening or lead-in period will be permitted (in addition to any parameters that require a confirmatory value).

The most current result prior to Randomization is the value by which study inclusion will be assessed, as it represents the participant's most current, clinical state.

Laboratory parameters and/or assessments that are included in [Table 1](#), Screening Procedural Outline may be repeated in an effort to find all possible well-qualified participants. Consultation with the Medical Monitor may be needed to identify whether repeat testing of any particular parameter is clinically relevant.

CONFIDENTIAL

The information contained herein may not be used, disclosed, or published without the written consent of Biogen MA Inc.

7. TREATMENT

Study treatment is defined as any investigational treatment(s), marketed product(s), placebo, or medical device intended to be administered to a study participant according to the study randomization or treatment allocation.

Study treatment includes both Investigational [Medicinal] Product (IP/IMP) and Non-investigational [Medicinal] Product (Non-IP/Non-IMP) as listed in the following table.

Study Treatment for Study 251PP301		
Medication	Potency	IP/Non-IP
BIIB092 ^a	50 mg/mL	IP
Placebo ^b (0.9% Sodium Chloride)	N/A	IP

IP = investigational product

^a Study treatment supplies may be labeled as BIIB092 or BMS-986168. The 2 study treatment names refer to an identical drug substance.

^b The 5% dextrose injection can be used if sodium chloride is not available.

An IP, also known as IMP in some regions, is defined a pharmaceutical form of an active substance or placebo being tested or used as a reference in a clinical study, including products already with a marketing authorization but used or assembled (formulated or packaged) differently than the authorized form, or used for an unauthorized indication, or when used to gain further information about the authorized form.

Other medications used as support or escape medication for preventative, diagnostic, or therapeutic reasons, as components of the standard of care for a given diagnosis, may be considered as non-investigational products.

A rescue medication such as EpiPen or Epi-kit (containing 1 mg/mL of epinephrine) will be dispensed for home care visits, for use in the event of an allergic reaction.

See [Table 6](#) for details regarding study treatments.

CONFIDENTIAL

The information contained herein may not be used, disclosed, or published without the written consent of Biogen MA Inc.

Table 6: Study Treatments for Study 251PP301

Product Description^a	Potency	IP/Non-IMP	Study Period	Packaging/Appearance	Storage Conditions (per label)
BIIB092 Injection, 1000 mg/vial ^b	50 mg/mL	IP	Double-blind	BIIB092 is supplied as a liquid drug product in glass vials containing an extractable dose per the DHA	Store refrigerated 2°C to 8°C Protect from light Do not freeze
BIIB092 Injection, 1000 mg/vial ^b	50 mg/mL	IP	Open-label extension	BIIB092 is supplied as a liquid drug product in glass vials containing an extractable dose per the DHA	Store refrigerated 2°C to 8°C Protect from light Do not freeze
BIIB092 Injection, 2000 mg/vial ^b	50 mg/mL	IP	Open-label extension	BIIB092 is supplied as a liquid drug product in glass vials containing an extractable dose per the DHA	Store refrigerated 2°C to 8°C Protect from light Do not freeze
Placebo (0.9% Sodium Chloride or 5% Dextrose) ^c	0.9% NaCl Or 5% dextrose	IP	Double-blind	Per product label	Per product label

DHA = Directions for Handling and Administration; IMP = investigational medicinal product; IP = investigational product; N/A = not applicable

^a BIIB092 dosage form and composition are provided in the DHA

^b BIIB092 is provided open-label to the unblinded pharmacist. After study treatment is prepared by the unblinded pharmacist all other study personnel will remain blinded to the identification of study treatment (BIIB092 vs. placebo) through Week 48.

^c Placebo is not provided by Biogen and obtained commercially by the site; storage should be in accordance with the product label.

CONFIDENTIAL

The information contained herein may not be used, disclosed, or published without the written consent of Biogen MA Inc.

7.1. Treatments Administered

The selection and timing of dose for each participant is as follows (Table 7):

Table 7: Selection and Timing of Dose

Study Treatment	Unit Dose Strength(s)/ Dosage Level(s)	Dosage Formulation Frequency of Administration	Route of Administration
BIIB092	2000 mg	Q4W	IV
Placebo	Matching dose volume at 0.9% NaCl or 5% Dextrose	Q4W	IV

IV = intravenous; Q4W = Once every 4 weeks.

7.2. Method of Treatment Assignment

All participants will be centrally randomized using an Interactive Response Technology (IRT). Before the study is initiated, each user will receive log in information and directions on how to access the IRT. Randomization will be stratified by country and screening CTT Part 2 stratum of a score either less than or equal to 170 seconds or greater than 170 seconds. Randomization will only be stratified by screening CTT Part 2 stratum under the IRT system for protocol Version 1. To promote treatment balance within each country, randomization will be stratified by both country and screening CTT Part 2 when the new IRT system for this protocol is in place.

Study treatment will be dispensed at the study visits as listed in Schedule of Activities (Section 2).

7.3. Blinding

Blinding of treatment assignment is critical to the integrity of this clinical study. However, in the event of a medical emergency or pregnancy in an individual participant in which knowledge of the investigational product is critical to the participant's management, the blind for that participant may be broken by the Investigator. The participant's safety takes priority over any other considerations in determining if a treatment assignment should be unblinded.

Before breaking the blind of an individual participant's treatment, the Investigator should determine that the unblinded information is necessary, i.e., that it will alter the participant's immediate management. In many cases, particularly when the emergency is clearly not related to the IP, the problem may be properly managed by assuming that the participant is receiving active product. It is highly desirable that the decision to unblind treatment assignment be discussed with the Medical Monitor, but the Investigator always has ultimate authority for the decision to unblind. The Principal Investigator should only call in for emergency unblinding AFTER the participant has made the decision to discontinue from study treatment.

For information on how to unblind in an emergency, consult the IRT manual.

CONFIDENTIAL

The information contained herein may not be used, disclosed, or published without the written consent of Biogen MA Inc.

In cases of accidental unblinding, contact the Medical Monitor and ensure every attempt is made to preserve the blind. The Bioanalytical Sciences section or its designate will be unblinded to the randomized treatment assignments in order to minimize unnecessary analysis of samples from control group participants.

Any request to unblind a participant for non-emergency purposes should be discussed with the Medical Monitor.

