8. DISCONTINUATION CRITERIA

8.1. Discontinuation From Study Treatment

Participants **MUST** discontinue study treatment (and non-IP at the discretion of the Investigator) for any of the following reasons:

- Participant's request to stop study treatment. Participants who discontinue study treatment and remain enrolled in the study will be expected to complete scheduled safety and efficacy evaluations until the decision is made to withdraw from the study.
- Any clinical AE, laboratory abnormality, or intercurrent illness which, in the opinion of the Investigator, indicates that continued participation in the study is not in the best interest of the participant
- Termination of the study by Biogen
- Loss of ability to freely provide consent through imprisonment or involuntary incarceration for treatment of either a psychiatric or physical (e.g., infectious disease) illness

In the case of pregnancy, the Investigator must immediately notify the Medical Monitor of this event and study treatment must be discontinued immediately. In most cases, the study treatment will be permanently discontinued in an appropriate manner (e.g., dose tapering if necessary for participant safety). Please call the Medical Monitor within 24 hours of awareness of the pregnancy. If the Investigator determines a possible favorable benefit/risk ratio that warrants continuation of study treatment, a discussion between the Investigator and the Medical Monitor/designee must occur.

If study treatment is discontinued prior to the participant's completion of the study, the reason for the discontinuation must be documented in the participant's medical records and entered on the appropriate CRF page.

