10.13. Unblinding for Medical Emergency

In a medical emergency when knowledge of the participant's treatment assignment may influence the participant's clinical care, the Investigator may access the participant's treatment assignment by IRT. The Investigator must document the reasons for unblinding in the participant's source documents. The Investigator is strongly advised not to divulge the participant's treatment assignment to any individual not directly involved in managing the medical emergency, or to personnel involved with the analysis and conduct of the study. The Investigator can contact Biogen to discuss such situations.

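### Protocol Section 7.3 makes emergency unblinding wait for the participant's decision to stop treatment, in conflict with the rest of 7.3 and with Section 10.13

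*Protocol*

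**What the plan says.** Protocol Section 7.3 lets the Investigator break the blind for an individual participant in two situations, a medical emergency or a pregnancy, when knowing the product is critical to management. It sets the order of priorities: "The participant's safety takes priority over any other considerations in determining if a treatment assignment should be unblinded". It asks the Investigator to confirm first that the information would change immediate management, and notes that in many cases "the problem may be properly managed by assuming that the participant is receiving active product". Prior discussion with the Medical Monitor is encouraged, but "the Investigator always has ultimate authority for the decision to unblind".

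The next sentence adds a condition on timing. The Principal Investigator "should only call in for emergency unblinding AFTER the participant has made the decision to discontinue from study treatment". The section then sends the reader to the IRT manual for the procedure.

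Section 10.13 covers the medical emergency again. When the assignment may influence care, "the Investigator may access the participant's treatment assignment by IRT". It adds a duty, "The Investigator must document the reasons for unblinding in the participant's source documents", and some advice: the Investigator is "strongly advised not to divulge the participant's treatment assignment to any individual not directly involved in managing the medical emergency". It contains no condition about discontinuation. Sections 7.3 and 10.13 do not refer to each other.

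**The concern.** A code-break procedure exists for the few cases in which clinical care depends on knowing the assignment. Section 7.3 has already narrowed the field to those cases by requiring that the information would change immediate management. The timing sentence then makes the call wait for something unrelated to clinical need, a decision by the participant to stop treatment.

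The person who has to make that decision may be unable to. Section 3 lists dysarthria and dementia among the features of PSP, and Appendix 2 plans for participants who lose capacity to consent. The provisions for a legally authorized representative (Section 6.1.1 and Appendix 2) concern consent, and neither 7.3 nor 10.13 brings them into the unblinding procedure. An investigator who followed the sentence as written, with an acutely unwell participant and no representative at hand, could lose time. What is at stake is patient safety, not the trial's error rate or power.

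**Working it through.** No arithmetic applies: the documents give no number of emergency unblinding cases, and the point depends on no statistical quantity. The check is a comparison of wording, all from the current Version 7 body text of the protocol.

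1. **Timing sentence against the priority statement in 7.3.** If safety outranks any other consideration in deciding whether to unblind, a prior decision about future dosing is one of the considerations it outranks. The timing sentence does not say so, and makes no exception for urgent need.

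2. **Timing sentence against the authority statement in 7.3.** The Investigator's authority is described as holding always. An authority that may be used only after someone else has decided a different question is conditional. The two sentences are adjacent and cannot both be followed literally.

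3. **7.3 against 10.13.** Both cover the medical emergency. Section 7.3 has the precondition. Section 10.13 requires that the reasons be documented, advises limiting disclosure, and stops there. With no cross-reference, a site has two rules and no statement of which prevails.

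4. **7.3 against the stopping rules.** The timing sentence assumes that the participant decides to stop.
   - *Participant request* is one reason for stopping in 8.1, and here the sentence fits.
   - *Adverse event, laboratory abnormality or intercurrent illness* is another. Here the stop follows when the event, "in the opinion of the Investigator, indicates that continued participation in the study is not in the best interest of the participant". The judgement is the Investigator's.
   - *Pregnancy*: 10.5 requires an immediate stop. Section 8.1 says the same, but goes on to allow for continuation if the Investigator sees a possibly favorable balance of benefit and risk and discusses it with the Medical Monitor.

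   So for the two situations in which 7.3 permits unblinding, discontinuation does not always depend on a decision by the participant.

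5. **When the sentence could cause delay.** All of these must hold together: the code is needed for immediate care; the participant has not decided to stop and cannot do so in time; no representative is at hand; and the Investigator reads the sentence as binding. The documents give no frequency for any of them.

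**The case against.** The strongest reply is that the text largely resolves the conflict itself. The sentence says *should*, the Investigator's authority is stated immediately before it, and 10.13 gives an independent route to the code. An investigator with an incapacitated participant therefore has explicit grounds to unblind at once. The clinical consequence may also be small. The acute reactions that the protocol foresees can be treated without the code: Section 14 sends hypersensitivity reactions to standard care, Section 7 supplies epinephrine for home visits, and no assignment-specific emergency treatment is mentioned. This stands. It means that delay is possible but not shown, and it limits the size of the point. It does not remove the contradiction, and an emergency instruction should not need reconciling during the emergency.

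The sentence may also serve a purpose: settling the dosing question before the assignment is known, so that knowledge of the assignment does not drive it. That aim is reasonable. Simply deleting the sentence would lose it, and Section 8.1 has no criterion for dosing after unblinding. Section 9.1 has the PSPRS, the primary scale, conducted by a neurologist and asks for the same CGI-C rater throughout where possible. An unblinded Investigator who also rates is therefore a real concern, and the advice in 10.13 on disclosure does not address it. This part of the objection shapes the fix.

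Two stronger readings are tempting. A reader might infer that the protocol forbids emergency unblinding until the participant agrees to stop. The wording is a recommendation, and 7.3 and 10.13 both let the Investigator act. A reader might also infer that every relevant stopping rule excludes the participant's choice, with pregnancy as an absolute case. Section 8.1 lists the participant's own request and leaves a route to continue in pregnancy; only 10.5 states the stop without exception.

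**Conclusion.** The conflict is real and can be read directly from the text. The timing sentence in 7.3 cannot be squared with the priority and authority statements beside it, or with the unconditional access in 10.13, and it does not always fit the stopping rules in 8.1 and 10.5. It is a conflicting instruction, not an absolute bar.

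Confidence is high for the inconsistency of wording and lower for its consequence. The IRT manual to which 7.3 refers is not among the documents, so it is not known whether calling in and IRT access are one step or two, or whether the manual repeats the condition. No rate and no actual harm is claimed. The point should be corrected because the sentence governs emergency care and the change is cheap.

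**What to change.** In Section 7.3, replace the sentence on when the Principal Investigator may call in with:

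> Where feasible, the decision on further study treatment should be made and documented before the blind is broken, but emergency unblinding must not be delayed for this decision. If the blind is broken first, the Investigator decides on further study treatment promptly with the Medical Monitor, and where possible a participant who stays in the study is rated by someone who does not know the assignment. See also Section 10.13.

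In Section 10.13, add the matching reference to 7.3. Check that the IRT manual agrees with both.

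The two sections also set different thresholds: 7.3 asks that the information will change management, while 10.13 asks only that it may influence care. The replacement does not settle that difference, which could be aligned at the same time.

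The cost is one sentence, one cross-reference and a check of the manual. There is one small downside: in rare cases an unblinded participant may remain on treatment. The prompt decision with the Medical Monitor and the rater safeguard limit the effect. Sample size, alpha and the planned analyses are unaffected.

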7.4. Dosage Modification

There will be no dose escalations or reductions of study treatment allowed.

Participants may be dosed within a ± 3 -day window for each dosing visit in the double-blind portion of the study after the first dose administered on Day 1 of Week 0. For the open-label extension period of the study, participants may be dosed within a ± 7 -day window for each dosing visit.

Participants should be carefully monitored for infusion reactions during administration. If an acute infusion reaction is noted, participants should be managed according to Section 14.

Dosing visits should generally not be skipped, only delayed. In the unusual circumstance where an extended delay occurs (e.g., 2 weeks or more), the Investigator should discuss this with the Medical Monitor.

7.5. Preparation/Handling/Storage/Accountability

Study treatment will be manufactured, handled, and stored in accordance with applicable Good Manufacturing Practice.

BIIB092 is supplied as a liquid drug product in glass vials containing an extractable dose per the Directions for Handling and Administration (DHA). The contents of the BIIB092 label will be in accordance with all applicable regulatory requirements. BIIB092 should not be used after the expiration date.

BIIB092 must be stored refrigerated between 2°C and 8°C with protection from light. Study treatment not supplied by Biogen will be stored in accordance with the package insert.

The product storage manager should ensure that the study treatment is stored in accordance with the environmental conditions (temperature, light, and humidity) as determined by the DHA. If concerns regarding the quality or appearance of the study treatment arise, the study treatment should not be dispensed, and Biogen should be contacted immediately.

The study treatment should be stored in a secure area according to local regulations. It is the responsibility of the Investigator to ensure that study treatment is only dispensed to study participants. The study treatment must be dispensed only from official study sites by authorized personnel according to local regulations.

Study site staff should follow the DHA for specific instructions on the handling, preparation, administration, storage, and disposal of the study treatment. The DHA will also describe the masking of the IV bags of study treatment (both BIIB092 and placebo) to maintain the treatment blind. The DHA supersedes all other references (e.g., protocol or Investigator's Brochure).

CONFIDENTIAL

The information contained herein may not be used, disclosed, or published without the written consent of Biogen MA Inc.

Investigational product documentation (whether supplied by Biogen or not) must be maintained to ensure drug is accurately administered. This includes documentation of drug storage, administration and, as applicable, storage temperatures, reconstitution, and use of required processes (e.g., required diluents, administration sets).

